2.2.2 Pharmacokinetic/pharmacodynamic variables

2.2.2.1 Pharmacokinetic variable

The PK variable is plasma concentration of bimekizumab. The assessment schedule for plasma concentration is available in [Table 2–1](#).

2.2.2.2 Pharmacodynamic variables

The PD variables are concentrations of cytokines of relevance to IL 17A/F signaling pathway and PsA biology, and include but are not limited to IL-17A, IL-17F, IL-23, IL-6, and tumor necrosis factor-alpha (TNF α).

2.2.3 Pharmacogenomic variables

Where local regulations permit, additional blood samples will be collected from consenting subjects at specific time points and stored at -80°C for up to 20 years to allow for potential, exploratory analyses of genomic, genetic, proteomic, and metabolite biomarkers relevant to disease biology and progression, response to therapy, and the inflammatory and immune response processes.

2.2.4 Immunological variables

Immunological variables allow evaluation of immunogenicity as well as immunological biomarkers.

- Anti-bimekizumab antibody (AbAb) detection prior to and following study treatment
- Serum complement concentrations.
- Flow cytometry analysis of key immune cell populations, including but not limited to CD3, CD19, CD4, CD8, and CD69 (using fluorescence activated cell sorting).
- Cytokines and other exploratory markers

2.2.5 Safety variables

Safety variables to be assessed as specified in [Section 10](#) are as follows:

- Incidence of AEs and serious adverse events (SAEs)
- Withdrawal due to AEs
- Change from Baseline in vital signs (blood pressure and pulse rate) and body weight
- Standard 12-lead electrocardiogram (ECG) intervals (RR, PR, QRS, QT, and QT intervals corrected for heart rate using Bazett's and Fridericia's formulas [QTcB and QTcF]), including changes from Baseline
- Change from Baseline in clinical laboratory variables (hematology, biochemistry, and urinalysis)

2.3 Study design and conduct

To be eligible to participate in this study, subjects must meet the following key inclusion criteria:

- Subject has a documented diagnosis of adult-onset PsA classified by CASPAR criteria with symptoms for at least 6 months prior to Screening with active PsA and must have at Baseline TJC ≥ 3 out of 78 and SJC ≥ 3 out of 76 (dactylitis of a digit counts as 1 joint each).
- Subject must be rheumatoid factor and anti-CCP antibodies negative.
- Subject must have active psoriatic lesion(s) and/or a documented history of psoriasis.

- Subjects may be TNF inhibitor naïve or may have received 1 prior TNF inhibitor. Subjects who have been on a TNF inhibitor previously must have:
 - experienced an inadequate response to previous treatment given for at least 3 months
 - been intolerant to administration (eg, had a side-effect/AE that led to discontinuation)
 - lost access to TNF inhibitor for other reasons

Two hundred subjects will be randomized to 1 of 5 treatment arms. Subjects in any treatment group who complete the 12-week Double-Blind Period will enter the 36-week Dose-Blind Period. Treatment during the Dose-Blind Period will start at Week 12 and be administered Q4W thereafter through Week 44.

Screening Period/ Baseline

During the Screening Period, the Investigator will obtain laboratory data and verify that the doses of methotrexate (MTX), leflunomide (LEF), nonsteroidal anti-inflammatory drugs (NSAIDs), or corticosteroids, if used, are stable. The Screening Period will also enable washout of medications not permitted for use during the study. The Screening Period will last 14 to 28 days.

Double-Blind Period

During the Double-Blind Period, subjects will be randomized 1:1:1:1:1 (stratified by region and prior TNF inhibitor exposure) to receive the following blinded study treatment regimens:

- Placebo
- Bimekizumab 16mg administered sc Q4W
- Bimekizumab 160mg administered sc Q4W
- Bimekizumab 320mg administered sc Q4W
- Bimekizumab 320mg loading dose followed by 160mg administered sc starting at Week 4 and Q4W thereafter

Enrollment of TNF inhibitor experienced subjects will be limited to approximately 30% of the total study population.

Investigational medicinal product (IMP) will be administered sc in the clinic at Baseline, Week 4, and Week 8. Additional non-dosing study visits in the Double-Blind Period will occur at Week 1 and Week 2. At Week 12, subjects will transition from the Double-Blind Period into the 36-week Dose-Blind Period. Note that the other assessments are planned to be performed before the IMP administration and will be analyzed for the Double-Blind Period.

Dose-Blind Period

The first IMP for the Dose-Blind Period will be administered at Week 12. At the Week 12 Visit, subjects will be allocated to bimekizumab treatment regimens as follows:

- Subjects in the placebo group will be rerandomized 1:1 to bimekizumab 160mg or bimekizumab 320mg Q4W

-
- Subjects in the bimekizumab 16mg dose group will be rerandomized 1:1 to bimekizumab 160mg or bimekizumab 320mg Q4W
 - Subjects in the bimekizumab 160mg dose group will continue to receive bimekizumab 160mg Q4W
 - Subjects in the bimekizumab 320mg dose group will continue to receive bimekizumab 320mg Q4W
 - Subjects in the bimekizumab 320mg (loading)/160mg dose group will continue to receive bimekizumab 160mg Q4W

All assessments for the Dose-Blind Period will be done from Week 18 to Week 48. The last IMP administration is on Week 44.

The total duration of treatment is 36 weeks.

During the 36-week Dose-Blind Period, subjects will be evaluated for inadequate response to treatment at defined time points. Subjects who do not show an improvement in tender and swollen joint count will be eligible to receive rescue therapy as defined in [Section 6.5](#).

Safety Follow-up/Extension study

At the completion of the Dose-Blind Period, Investigators should discuss treatment options with the subject. Subjects will be given the opportunity to enter an extension study at Week 48, provided they do not qualify for rescue therapy.

Table 2-1: Schedule of assessments

Protocol activity	Visit ^a / Week	Screening (V1) (14-28 days)	Baseline (Day 1, V2) (first dose)	Double-Blind Period (weeks after first dose)			Dose-Blind Period (weeks after first dose)						SFU ^b							
				3	4/5/6/8	7/12	9/	1/1/2/2/4	1/2/3/3/6	1/4/4/0	16/48	ET								

k It is recommended that Quantiferon TB GOLD test be performed.

l At Weeks 16, 24, and 36, subjects will be evaluated for inadequate response to treatment. Subjects who do not show an improvement in tender and swollen joint counts will be eligible to receive rescue therapy.

m If a subject has had a recent radiograph of the chest within 3 months prior to the Screening Visit, it may be used as the Screening chest x-ray.

n Hand and foot x-rays are not required if the subject has hand and/or foot x-rays (only hand OR foot is required) that are no more than 2 years from the date of Screening, and are available for submission within the Screening Period to the central radiology reader and whose reading is consistent with CASPAR Criteria #5 showing ill-defined ossification near joint margin (but excluding osteophyte formation). For those subjects without prior x-rays that meet this Criterion and those whose submitted films are not read with changes consistent with CASPAR, hand and foot x-rays may be done during the Screening Period.

o IXRS is used to register the Subject at Screening, randomize the Subject at Baseline/Day 1, rerandomize the Subject at Week 12 (Subjects in the placebo or bimekizumab 16mg treatment groups), and to register all visits

p The minimum time between doses during the Double-Blind Period should be no less than 25 days and no more than 31 days and during the Dose-Blind Period should be no less than 24 days and no more than 32 days.

q At Week 12, the Dose-Blind Period dosing will start.

2.4 Determination of sample size

A total of 200 subjects (40 in each treatment group) are planned to be randomized in this study.

The sample size is calculated based on the ACR50 response data from the Phase 2 bimekizumab study in subjects with PsA (PA0007). The ACR50 responses at Week 12 were reported to be 80.0% (95% CI: 37.6%; 96.4%), 52.6% (95% CI: 31.7%; 72.7%), and 33.3% (95% CI: 9.7%; 70.0%) for the bimekizumab 560/320mg, bimekizumab 240/160mg, and bimekizumab 80/40mg doses, respectively. Placebo ACR50 response at Week 12 is based on the PA0007 study (0%), the FUTURE 1 study (8.0%; Mease et al, 2015) and FUTURE 2 study (6.0%; McInnes et al, 2015).

Since the uncertainty of ACR50 responder rates of PA0007 is high due to the small number of subjects, the midpoint of the point estimate and the lower 95% CI was used for the sample size calculation of all active dose groups as a conservative assumption. For the bimekizumab 16mg dose, the midpoint of the 80/40mg dose was reduced by 6.5%.

Hence, ACR50 responder rates of 58.5%, 42.2%, 15.0%, and 8% at the end of a 12-week treatment period for bimekizumab 320mg, bimekizumab 160mg, bimekizumab 16mg, and placebo have been assumed, respectively. Since those ACR50 responder rates are based on a study population of TNF inhibitor naïve subjects, an adjustment was made for a reduction in ACR50 response of 25% by a maximum of 30% of subjects with TNF inhibitor experience (ie, 12 subjects per group).

The sample size for the primary objective of evaluating the dose response relationship was calculated using a 2-sided test for detecting a linear trend across proportions (Nam, 1987) at a 2-sided significance level of 0.05. With 40 subjects in each treatment group, the test for detecting the overall dose response based on ACR50 response is powered at >99%.

The sample size calculations were performed using the software nQuery Advisor® 7.0.

3 DATA ANALYSIS CONSIDERATIONS

3.1 General presentation of summaries and analyses

All computations and generation of outputs will be performed using SAS® Version 9.3 or later. All tables and listing will use Courier New font size 9.

All original and derived variables will be listed and described using summary statistics (number of observations [n], mean, standard deviation [SD], median, minimum and maximum, unless otherwise stated) or frequency counts (number of subjects [N] and percentages). For multiple post-Baseline assessments at a specific visit, the first non-missing measurement will be used for summary statistics or frequency counts.

Descriptive statistics will be displayed to provide an overview of the study results. For categorical variables, the number and percentage of subjects in each category will be presented. The denominator for percentages will be based on the number of subjects appropriate for the purpose of analysis. Unless otherwise noted, all percentages will be displayed to 1 decimal place. No percentage will be displayed for zero counts, and no decimal will be presented when the percentage is 100%. For continuous variables, descriptive statistics will include number of subjects with available measurements (n), mean, SD, median, minimum, and maximum.

Decimal places for descriptive statistics will always apply the following rules:

- “n” will be an integer.
- Mean, SD, and median will use 1 additional decimal place compared to the original data.
- Coefficient of variance (CV[%]) will be presented with 1 decimal place.
- Minimum and maximum will have the same number of decimal places as the original value.

Statistical tests of efficacy variables will be presented as 2-sided p-values rounded to 3 decimal places. P-values less than 0.001 will be presented as “<0.001” and p-values greater than 0.999 will be presented as “>0.999” Statistical comparisons will be performed by two-sided statistical tests at the 0.050 level of significance.

The SAS output for Cochran-Mantel-Haenszel test, logistics regression, and analysis of covariance (ANCOVA), as well as multiple imputation (MI) will be provided as a separate PDF document in addition to TFLs. The SAS output will be included in the ‘Documentation of Statistical Methods’ section of the clinical study report.

In the Double-Blind Period the order of treatment groups will be presented in tables from left to right will be

- Placebo
- Bimekizumab 16mg
- Bimekizumab 160mg
- Bimekizumab 160mg with loading dose 320mg
- Bimekizumab 320mg

The general principle is to go from the lowest to highest dose when moving from left to right. Tables may also include columns for all subjects or all subjects on bimekizumab. An overview of the treatment group assignment is available in [Section 12.3](#).

Selected tables which are specified in the TFL shells will only use data from the Dose-Blind Period. For listings and the selected tables, the label and order of treatment groups will be presented as follows:

- Placebo to bimekizumab 160mg at Week 12
- Placebo to bimekizumab 320mg at Week 12
- Bimekizumab 16mg to bimekizumab 160mg at Week 12
- Bimekizumab 16mg to bimekizumab 320mg at Week 12
- Bimekizumab 160mg with loading dose 320mg to bimekizumab 160mg at Week 12
- Bimekizumab 160mg
- Bimekizumab 320mg

The abbreviation for bimekizumab is BKZ and will be used in tables and listings headers. In the TFLs subjects on bimekizumab 160mg with loading dose 320mg will be displayed as “BKZ 160mg w/LD”. All subjects on bimekizumab will be labeled as “All BKZ” in the TFLs.

A complete set of data listings containing all documented data and all derived data (eg, change from Baseline) will be generated.

Unless otherwise stated, listings will be sorted by treatment, subject number within each treatment group (not randomization number), variable (if applicable) and visit (if applicable; including timing relative to dosing if applicable). For listings including nonrandomized subjects, the nonrandomized subjects will be shown first in the listing, ordered by subject number. All listings will include repeat and unscheduled measurements; such measurements will appear in chronological order together with the scheduled visits, ie, a repeated measurement will appear directly after the visit and time relative to dosing for which the repeat measurement was performed. In all the listings dates will be presented in the format 'YYYY-MM-DD' and times will be presented in 24h clock format as 'hh:mm'.

3.2 General study level definitions

3.2.1 Relative day

Relative day will be calculated as the current date minus the date of first dose of study drug administration plus 1 for days on or after the day of first dose of study drug dose. Relative day 1 is the date of first bimekizumab administration.

Relative days before first administration of bimekizumab will have the prefix '-' and will be calculated as date of first dose of study drug administration minus the current date.

For days after the last bimekizumab administration, relative day will be calculated as the current date minus the date of last dose of study drug administration including the prefix '+'.

Calculations of 'Relative Day' should not include partial dates, but should be left blank in these instances.

For AEs, relative days for start and stop dates will be calculated as the number of days since the first injection of the medication. For non-treatment emergent AEs, relative day of onset will be negative if the event started and stopped before the first dose. A complete date must be established in order to correctly identify the AEs. [Section 4.2.2](#) describes imputation rules in case of missing data for AEs.

3.2.2 Study Periods

The following study periods are defined for the classification by study period:

- Pre-treatment period (Screening period): up to 28 days, ends with the visit date of the first dose of study medication (Visit 2)
- Double-Blind treatment period: starts with the visit date of the first dose of study medication (Visit 2), ends at Week 12 visit date
- Dose-Blind treatment period: starts at the Week 12 visit, ends at Week 48 visit.
- Post-treatment period: the post-treatment period (Follow-up period) is the period after the Week 48 visit

3.3 Definition of Baseline values

The last valid measurement before first dose of study drug (Visit 2) will be used as the Baseline value. If a scheduled Baseline assessment is taken on the same day and after the first

administration of study medication, it will be analyzed as the first post-Baseline assessment. If a scheduled Baseline assessment is taken on the same day as first administration of study medication and no time is collected, it will be assumed to have been taken prior to study medication.

The exception of the above rule are the questionnaires collected from the vendor ERT and measurements for CRP and hs-CRP. For those measurement, the last valid measurement at the same day as Visit 2 will be used as the Baseline value.

However, for some variables, assessments may be scheduled for Screening only and not for Baseline. In this case the Screening value will be utilized as Baseline value. If a Baseline measurement is missing, and a Screening value available, the Screening value will be utilized as Baseline instead.

3.4 Protocol deviations

Important protocol deviations are defined as those deviations from the protocol likely to have a meaningful impact on the primary efficacy outcomes for an individual subject. Important protocol deviations will be identified and classified by the deviation types defined in the appropriate protocol-specific document. All protocol deviations will be reviewed as part of the ongoing data cleaning process and all important deviations will be identified and documented prior to unblinding to confirm exclusion from Per Protocol Set (PPS), Pharmacokinetics Per-Protocol Set (PK-PPS) and Pharmacodynamics Per-Protocol Set (PD-PPS). The exclusion from PPS is limited to the Double-Blind Period, ie. only subjects with important protocol deviations prior to re-randomization at Visit 7 (Week 12) will be excluded from PPS. Subjects with important protocol deviations after Visit 7 (Week 12) will not be excluded from PPS.

3.5 Mapping of assessments performed at early termination visit

Study assessments at an early termination visit where visit date matches the visit date of a scheduled visit will be summarized at the scheduled visit with the same visit date. Premature study termination visit assessments that do not have a scheduled visit with a matching date will be assigned to the next scheduled site visit following the last visit where assessments were available regardless whether or not there will be an assessment on this visit. The assessment of AbAb is an exception to this rule: AbAb will be mapped to the next visit where antibody levels are measured. For subjects who discontinue study treatment early and return for the Week 12 visits as per the protocol, the assessments collected at that visit are summarized as Week 12 assessments.

3.6 Analysis sets

The primary efficacy variable will be analyzed for all subjects in the Full Analysis Set (FAS). The supportive analyses for the primary efficacy variables will include the Randomized Set (RS) and PPS. All other efficacy variables will be based on the FAS. Demographics tables will be performed for FAS, Safety Set (SS), and Dose-Blind Set (DBS). Safety variables will be summarized using the SS. In addition, safety analyses during the Dose-Blind Period will be conducted on all subjects in the DBS. PK variables will be analyzed for all subjects in the PK-PPS. PD variables will be analyzed for all subjects in the PD-PPS.

At the time of the Week 48 interim it was discovered that the Dose-Blind Responder Set (DBRS) and Escape Subject Set (ESS) were defined incorrectly from the original intent. The original

intent of the ESS analysis set was to have only those subjects that were eligible to receive rescue therapy, that went on to actually receive rescue therapy, with all other subjects remaining in the DBRS. As such, two extra sets, the Corrected Dose-Blind Responder Set (cDBRS) and Corrected Escape Subject Set (cESS) have been added. These analysis sets will correctly select out those subjects that were eligible and received rescue medication. All outputs created on the DBRS and ESS will also be produced on the cDBRS and cESS to give full transparency of the difference. Further all outputs using the DBRS and ESS will be repeated on the DBS and this analysis will be used as the main analysis of the Dose-Blind as this analysis set is the most unbiased set.

3.6.1 Enrolled Set (ES)

The Enrolled Set (ES) will consist of all subjects who have given informed consent.

3.6.2 Randomized Set (RS)

The RS consists of all randomized subjects.

3.6.3 Safety Set (SS)

The SS consists of all randomized subjects who received at least 1 dose of the IMP.

3.6.4 Full Analysis Set (FAS)

The FAS consists of all randomized subjects who received at least 1 dose of the IMP and have valid measurement of the primary efficacy variable at Baseline.

3.6.5 Per-Protocol Set (PPS)

The PPS consists of all subjects in the FAS who had no important protocol deviation affecting the primary efficacy variable. The subjects with important protocol deviations will be predefined and evaluated during a data evaluation meeting prior to unblinding of the data.

3.6.6 Pharmacokinetics Per-Protocol Set (PK-PPS)

The PK-PPS is a subset of the FAS, consisting of those subjects who had no important protocol deviations affecting the pharmacokinetic variables, as confirmed during ongoing data cleaning meetings prior to database lock.

3.6.7 Pharmacodynamics Per-Protocol Set (PD-PPS)

The PD-PPS consists of all randomized subjects who took at least one dose of the IMP and provided at least 1 PD measurement post-dose that is without important protocol deviation affecting that time point.

3.6.8 Dose-Blind Set (DBS)

The DBS consists of all subjects who started the Dose-Blind Period and who received at least 1 dose of IMP during the Dose-Blind Period.

3.6.9 Escape Subject Set (ESS)

The ESS consists of all subjects who started the Dose-Blind Period and who received at least 1 dose of the IMP during the Dose-Blind Period and who have not achieved at least a 10% reduction from Baseline in SJC and TJC at Week 16, Week 24, or Week 36.

3.6.10 Dose-Blind Responder Set (DBRS)

The DBRS consists of all subjects who started the Dose-Blind Period and who received at least 1 dose of the IMP during the Dose-Blind Period and who have achieved at least a 10% reduction from Baseline in SJC and TJC at Week 16, Week 24, and Week 36.

3.6.11 Corrected Escape Subject Set (cESS)

The cESS is a corrected version of the ESS, which was incorrectly defined previously. The cESS consists of subjects that have shown less than a 10% improvement in SJC and TJC at either Week 16, Week 24, or Week 36 and received rescue therapy.

3.6.12 Corrected Dose-Blind Responder Set (cDBRS)

The cDBRS is a corrected version of the DBRS, which was incorrectly defined previously. The cDBRS consists of subjects that have shown at least a 10% improvement in SJC or TJC at Week 16, Week 24 and Week 36. Subjects that would be in the cESS, including subjects that discontinued, that did not receive rescue therapy will be in the cDBRS.

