### **15.1 Definition of analysis sets**

The Enrolled Set (ES) will consist of all subjects who have given informed consent.

The Randomized Set (RS) consists of all randomized subjects.

The Safety Set (SS) consists of all randomized subjects who received at least 1 dose of the IMP.

The Full Analysis Set (FAS) consists of all randomized subjects who received at least 1 dose of the IMP and have valid measurement of the primary efficacy variable at Baseline.

The Per-Protocol Set (PPS) consists of all subjects in the FAS who had no important protocol deviation affecting the primary efficacy variable. The subjects with important protocol deviations will be predefined and evaluated during a data evaluation meeting prior to unblinding of the data.

The Pharmacokinetic Per Protocol Set (PK-PPS) is a subset of the FAS, consisting of those subjects who had no important protocol deviations affecting the pharmacokinetic variables, as confirmed during ongoing data cleaning meetings prior to database lock.

The PD-PPS consists of all randomized subjects who took at least one dose of the IMP and provided at least 1 PD measurement post-dose that is without important protocol deviation affecting that time point.

The Dose-Blind Set (DBS) consists of all subjects who started the Dose-Blind Period and who received at least 1 dose of IMP during the Dose-Blind Period.

The Escape Subject Set (ESS) consists of all subjects who started the Dose-Blind Period and who received at least 1 dose of the IMP during the Dose-Blind Period and who have not achieved at least a 10% reduction from Baseline in SJC and TJC at Week 16, Week 24, or Week 36.

The Dose-Blind Responder Set (DBRS) consists of all subjects who started the Dose-Blind Period and who received at least 1 dose of the IMP during the Dose-Blind Period and who have achieved at least a 10% reduction from Baseline in SJC and TJC at Week 16, Week 24, and Week 36. Subjects who are eligible for the ESS but do not receive rescue medication, remain in the DBRS.

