4.3.2.2 Changes during interim analysis to SAP-defined analyses

At the time of the Week 48 interim it was discovered that the DBRS and ESS were defined incorrectly from the original intent. The original intent of the ESS analysis set was to have only those subjects that were eligible to receive rescue therapy, that went on to actually receive rescue therapy, with all other subjects remaining in the DBRS. As such, two extra sets, the cDBRS and cESS have been added. These analysis sets will correctly select out those subjects that were eligible and received rescue medication. For the final analysis, all outputs created on the DBRS and ESS will also be produced on the cDBRS and cESS to give full transparency of the difference. Further all outputs using the DBRS and ESS will be repeated on the DBS and this analysis will be used as the main analysis of the Dose-Blind as this analysis set is the most unbiased set.

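### The corrected responder set (cDBRS) leaves out unrescued Dose-Blind subjects with no observed failure who lack a joint count at Week 16, 24 or 36, contrary to its stated intent

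*SAP*

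**What the plan says.** SAP Sections 3.6 and 4.3.2.2 explain that the two Dose-Blind subsets had been defined wrongly. The escape set was meant for subjects eligible for rescue "that went on to actually receive rescue therapy, with all other subjects remaining in the DBRS". Two corrected sets were added for this purpose.

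- **cESS** (SAP 3.6.11): subjects who "have shown less than a 10% improvement in SJC and TJC at either Week 16, Week 24, or Week 36 and received rescue therapy".
- **cDBRS** (SAP 3.6.12), route 1: "The cDBRS consists of subjects that have shown at least a 10% improvement in SJC or TJC at Week 16, Week 24 and Week 36".
- **cDBRS**, route 2: "Subjects that would be in the cESS, including subjects that discontinued, that did not receive rescue therapy will be in the cDBRS".

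Protocol Section 15.1 carries a shorter form of the same intent: "Subjects who are eligible for the ESS but do not receive rescue medication, remain in the DBRS". None of these places says how a missing joint count affects membership.

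Under SAP Section 8.3 the other efficacy variables are produced on the FAS, DBRS, ESS, cDBRS, cESS and DBS. For the repeat on the DBS, Section 3.6 states that "this analysis will be used as the main analysis of the Dose-Blind as this analysis set is the most unbiased set". The disposition table in SAP Section 5.1 counts the DBS, ESS and DBRS, but neither corrected set.

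**The concern.** The intent describes two complementary sets: eligible and rescued subjects in one, everyone else in the other. The cDBRS text instead asks for improvement actually shown at three visits, then adds back subjects who would have qualified for the cESS but had no rescue. Someone who improved whenever examined, had no rescue, and missed one joint count satisfies neither part.

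At stake are the cDBRS denominators and any statement that the two corrected sets together account for the Dose-Blind population. The disposition table as specified would not reveal a shortfall, because it omits both sets. The sets were added at the Week 48 interim, after treatment codes had been released to sponsor personnel for the Week 12 interim (SAP 4.3.1). Membership is therefore better fixed in the text than left to programming judgement.

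**Working it through.** The plan gives no figure to reproduce. The check is logical, with an illustrative calculation at the end.

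**Inputs**
- DBS: started the Dose-Blind Period and had at least one dose in it; no joint-count condition (SAP 3.6.8).
- cESS and cDBRS rules as quoted above (SAP 3.6.11, 3.6.12).
- After Week 12, a subject withdrawn from treatment has only an Early Termination (ET) visit and the safety follow-up visit (Protocol 6.3).
- ET data without a matching scheduled date go to the next scheduled visit after the last one attended (SAP 3.5).
- Missing binary outcomes are handled by NRI (SAP 4.2.1, 8.3).
- Dose-Blind dropout or missed-visit rate: not given. Shares of 5% to 20% are assumed below.

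**Step 1: enumerate.** Code each of Weeks 16, 24 and 36 as I (at least 10% improvement in SJC or TJC), F (less than 10% in both) or M (missing). I and F are exact complements. Crossing 3 × 3 × 3 = 27 patterns with rescue (yes/no) and discontinuation (yes/no) gives 27 × 2 × 2 = 108 logical cells. These are cells, not subjects.

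**Step 2: complete counts.** Pattern III enters the cDBRS by route 1. Any pattern with an F goes to the cESS if rescued and to the cDBRS by route 2 if not. There is no gap, and no overlap in any of the 108 cells. The defect arises only through missing counts.

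**Step 3: missing counts, no observed failure.** The patterns made of I and M only number 2 × 2 × 2 = 8. Removing III leaves 7: IIM, IMI, IMM, MII, MIM, MMI, MMM. Without rescue, these give 7 × 2 = 14 cells.
- *Literal reading of route 2* (the words on discontinuation qualify subjects who would be in the cESS, hence subjects with an observed failure): all 14 cells fall in neither set.
- *Wider reading* (every unrescued subject who discontinued is included): the 7 discontinued cells enter the cDBRS. The 7 cells for subjects who stayed in the study remain outside.

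Rescue without an observed failure would depart from Protocol Section 5.1.4 and is left aside; the fix covers it too.

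**Step 4: what ET mapping fills.** A last visit at Week 32 sends the ET count to Week 36, so that subject can be complete. Last visits at Weeks 12, 16, 20, 24 and 28 send it to Weeks 16, 20, 24, 28 and 32, and Week 36 stays empty. If a mapped count at Week 16, 24 or 36 is a failure, the unrescued dropout enters the cDBRS by route 2 on either reading.

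**Step 5: effect on a response rate.** Let r be the rate in the intended set (DBS minus cESS), m the share of that set left out, and q the share of those left out who respond at the visit. The rate shown is (r − m·q)/(1 − m). With r = 50% (assumed):

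| m | q = 0 | q = 50% | q = 100% |
|---|---|---|---|
| 5% | 0.50/0.95 = 52.6% | 0.475/0.95 = 50.0% | 0.45/0.95 = 47.4% |
| 10% | 0.50/0.90 = 55.6% | 0.45/0.90 = 50.0% | 0.40/0.90 = 44.4% |
| 20% | 0.50/0.80 = 62.5% | 0.40/0.80 = 50.0% | 0.30/0.80 = 37.5% |

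The rate rises when q is below r and falls when q is above it. Dropouts who left before Week 36 have no Week 48 data, so NRI sets q = 0 for them at Week 48. For subjects who only missed a visit, q can take any value.

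**The case against.** The strongest reply is that the second sentence of Section 3.6.12 names discontinued subjects as belonging to the cDBRS, and that the intent, stated in both Section 3.6 and Section 4.3.2.2, tells a programmer how to resolve any doubt. ET mapping fills some of the empty visits. The cDBRS outputs are supplementary, largely by-visit summaries, at time points that Protocol Section 4.1.3 calls exploratory.

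Much of this stands, and it rules out several stronger inferences a reader might draw:

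- *That dropouts as a group disappear from the corrected sets.* Unrescued dropouts with an observed failure are in the cDBRS on either reading. Those without one are lost only on the literal reading.
- *That cDBRS rates are inflated.* Direction depends on who is missing, as Step 5 shows. A rise follows only for dropouts at Week 48.
- *That the SAP's aim of transparency is defeated.* That remark in Section 3.6 concerns showing results on the old and corrected sets side by side. It does not promise that the corrected sets add up to the DBS.
- *That the main results are at risk.* The DBS analysis keeps every subject concerned, and the Week 12 primary analysis uses the FAS (SAP 8.1.2).

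What the reply does not answer is the subject who stays in the study, never fails, and misses a count. The second sentence does not reach that subject on any reading, and an intent stated elsewhere does not change the membership rule as written.

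**Conclusion.** The point holds, as a minor one. The cDBRS rule contradicts the intent given for it. An unrescued subject without an observed failure who lacks a joint count at Week 16, 24 or 36 belongs to neither corrected set. This is certain for missed visits; for dropouts it rests on the literal reading of a sentence that can be programmed two ways.

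The size is unknown, because it depends on a Dose-Blind dropout and missed-visit rate that the documents do not give. The 37.5% to 62.5% span in the table comes from assumed inputs (a 50% rate, 5% to 20% of subjects left out, none to all of them responding) and is not an estimate of bias. The consequence is confined to the supplementary cDBRS outputs.

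**What to change.** In SAP Section 3.6.12, define the cDBRS as all DBS subjects who are not in the cESS. State that a missing joint count does not affect membership, so that cESS plus cDBRS equals the DBS; Section 3.6.11 should say that the cESS is drawn from the DBS. Under this definition no cell of the enumeration is left over. Add the cESS and cDBRS to the disposition table in SAP Section 5.1 so that the sum can be seen.

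The cost is about one sentence of text, one changed membership flag and two more sets in the disposition table. No new data are needed, and neither the main Dose-Blind analysis nor the Week 12 analysis changes.
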